1.1 Background

Since its initial description in 2010, POEM has been suggested to be a safe and effective surgery for achalasia and other esophageal motility disorders.^{1,2} Compared to patients who undergo the traditional laparoscopic Heller myotomy, patients managed with POEM experience shorter procedure times, longer myotomies, lower adverse events, and improved functional outcomes.³ However, postoperative retrosternal pain and regurgitation due to residual carbon dioxide and/or increased intraoperative esophageal exposure to gastric acid remain common. Dual innervation of the esophagus by vagal and spinal afferent fibers is present along the entire length of the esophagus, accounting for patients' reports of vague discomforts and localized retrosternal sensations, respectively.⁴ Pain management has largely been based on opioids, which may contribute to worsened symptoms associated with achalasia.⁵ Postoperatively, most patients typically experience mild to moderate pain requiring modest doses of opioids.⁶

1.2 Investigational Agent

We recently published a case report on opioid-free anesthesia for POEM surgery utilizing magnesium not only for its analgesic,⁷ but also antispasmodic properties.^{8,9} Magnesium has been recognized as an antinociceptive agent since 1916, but its mechanism of action remains poorly elucidated. Two of its functions were considered for this anesthetic plan. First, magnesium is a noncompetitive N-methyl-D-aspartate (NMDA) receptor antagonist that can decrease visceral hyperalgesia.⁷ Second, magnesium induces smooth muscle relaxation by decreasing intracellular calcium concentrations in both smooth muscle and the adrenal gland, the latter causing a decrease in circulating catecholamines.¹⁰ Magnesium has been well characterized in obstetrical management of preeclampsia.⁸ The antispasmodic potential of magnesium was recently studied in the context of bladder surgery, where intraoperative magnesium administration was associated with decreased catheter-related bladder discomfort and improved patient satisfaction.⁹ In POEM procedures, insufflation with carbon dioxide for visualization can lead to postoperative subcutaneous or mediastinal emphysema. Residual carbon dioxide along the esophagus can also lead to referred pain that translates as postoperative esophageal spasm and regurgitation. Magnesium may adequately relax esophageal smooth muscle and desensitize afferent nerve endings to decrease these symptoms. In other words, the mechanisms underlying magnesium provide a physiologically and anatomically targeted therapy for esophageal pain.

1.3 Preclinical Data

None

CONFIDENTIAL

This document is confidential and the property of Stanford University School of Medicine.

1.4 Clinical Data to Date

Magnesium has been extensively studied for its nonopioid analgesic properties across multiple different types of surgeries and procedures in the anesthesia literature.¹¹ Its smooth muscle relaxant properties have been also documented in the context of preeclampsia management in obstetrics.¹² We also recently published a case report that highlighted the role of magnesium in decreasing postoperative pain specific to esophageal spasms and reflux.¹³

1.5 Dose Rationale and Risk/Benefits

The magnesium bolus dosing of 50 mg/kg emulates the dose used in a recent urologic study that explored the effect of magnesium to decrease bladder catheter-associated discomfort.⁹ Furthermore, this bolus dose and the infusion rate are the most frequently reported dose/rate in a meta-analysis of 20 randomized controlled trials.¹² The aforementioned meta-analysis found no major adverse events associated with magnesium toxicity, whilst finding a statistically and clinically significant decrease in postoperative pain. The medication is administered intravenously as part of the intraoperative anesthetic regimen. The POEM surgery lasts on average 1 to 2 hours, which is the maximum duration of the magnesium infusion. This will limit the risk of magnesium toxicity. Hence, the study will be safely investigating a nonopioid analgesic that has been shown to be efficacious in similar populations undergoing a diverse range of surgeries, with the hope of clarifying the antispasmodic potential of magnesium.

2 Study Objectives

Primary Objective

To assess the efficacy of magnesium sulfate on decreasing esophageal spasm-associated pain as measured by subjective pain scores and the esophageal symptoms questionnaire score.¹⁴

Secondary Objective

To assess the efficacy of magnesium sulfate on decreasing intraoperative opioid usage.
 To assess the efficacy of magnesium sulfate on decreasing postoperative opioid consumption.
 To assess the efficacy of magnesium sulfate on decreasing discharge opioid prescription.
 To assess the efficacy of magnesium sulfate on decreasing postoperative pain as measured by the esophageal symptoms questionnaire score at 24 hours.

3 Study Design

3.1 General Design

- Prospective randomized, double-blind, placebo-controlled trial
- Expected duration of subject participation: 2 days

3.2 Primary Study Endpoints

This study will evaluate the efficacy of magnesium sulfate on decreasing esophageal spasm-associated pain as measured by subjective pain scores and the esophageal symptoms questionnaire score.

CONFIDENTIAL

This document is confidential and the property of Stanford University School of Medicine.

3.3 Secondary Study Endpoints

This study will assess the efficacy of magnesium sulfate on decreasing intraoperative opioid usage, postoperative opioid consumption, discharge opioid prescription, and on decreasing postoperative pain as measured by the esophageal symptoms questionnaire score at 24 hours.

4 Subject Selection and Withdrawal

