4.1 Inclusion Criteria

- i) Ages 18 and over
- ii) Subjects capable of giving informed consent, or have an acceptable surrogate capable of giving consent on the subject's behalf
- iii) Planned peroral endoscopic myotomy

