4.2 Exclusion Criteria

- i) cannot give consent
- ii) patients who are clinically unstable and/or require urgent/emergent intervention
- iii) previous esophageal myotomy
- iv) preexisting hypermagnesemia
- v) end-stage renal disease
- vi) neuromuscular disease, including but not limited to Guillain-Barre syndrome, myasthenia gravis, congenital myopathy, and muscular dystrophy
- vii) preexisting heart failure
- viii) severe ventricular systolic dysfunction (left or right ventricle)

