5.6 Prior and Concomitant Therapy

Information on their preoperative medications will be collected, including use of multivitamins, herbal supplements, or magnesium-containing supplements, and use of acid-reducing medications such as H2-receptor antagonists or proton pump inhibitors.

During the study, the patients will be expected to receive standard anesthetic care including hypnotics, narcotics, neuromuscular blockers (e.g. succinylcholine/rocuronium), antiemetics, vasopressors, antihypertensives, and anesthetics as needed at the anesthesia team's discretion. In the rare case of magnesium toxicity, all healthcare providers will have access to calcium chloride/gluconate therapy to reverse the cardiorespiratory and musculoskeletal effects.

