7.2 Statistical Methods

Data will be expressed as means \pm SD, number (proportion), relative risk, 95% CI, absolute risk reduction, or number needed to treat.

The primary outcome is the incidence of esophageal spasm-related pain at 0 h postoperatively, compared using the chi-square test.

The secondary outcomes of the incidence of esophageal spasm-related pain at 24 hours postoperatively, intraoperative opioid usage, postoperative opioid consumption, and discharge opioid prescription will be compared using the chi-square test or Fisher's exact test as appropriate. Continuous variables will be compared using the Mann–Whitney *U* test. Categorical variables will be compared using the chi-square test or Fisher's exact test as appropriate.

Post hoc subgroup analyses will be conducted regarding the incidence of esophageal spasm-related pain according to achalasia type (e.g. type 1, 2, or 3), preoperative H2-receptor antagonist use, preoperative proton pump inhibitor use, and intraoperative opioid usage. *Post hoc* subgroup analysis will be further conducted on postoperative magnesium levels and the incidence of esophageal spasm-related pain at 24 hours.

All *P* values will be two-sided, and a value of $P < 0.05$ will be considered statistically significant.

Comparisons of postoperative pain between the two groups at time 0 h and time 24 h will be analyzed using the Mann–Whitney *U* test and performed using an adjusted significance level of 0.0125 (0.05/4) after *post hoc* analysis using the Bonferroni method.

Statistical analyses will be performed using R version 4.0.3.

CONFIDENTIAL

This document is confidential and the property of Stanford University School of Medicine.

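### Preoperative opioid users are eligible but the discharge opioid endpoint takes no account of home use; if any prescription counts, the contrast between arms is diluted

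*Combined protocol and SAP*

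**What the plan says.** - **Eligibility.** Section 4.1 has three inclusion items: adult age, consent, and "Planned peroral endoscopic myotomy". None of the eight exclusion items in 4.2 mentions opioid use. Patients on opioids before surgery can therefore be enrolled.
- **Endpoint.** Sections 2 and 3.3 aim at "decreasing intraoperative opioid usage, postoperative opioid consumption, discharge opioid prescription", so three of the four secondary objectives concern opioids. Neither these sections nor 7.2 says whether the discharge endpoint means any, a new or an increased prescription.
- **Test.** Under 7.2, "discharge opioid prescription will be compared using the chi-square test or Fisher's exact test as appropriate". No adjustment or stratification is given. The listed subgroups concern pain, and preoperative opioid use is not among them.
- **Analysis set.** Section 7.3 keeps every randomized patient, so home opioid users stay in the comparison.
- **Baseline data.** Section 5.6 states: "Information on their preoperative medications will be collected, including use of multivitamins, herbal supplements, or magnesium-containing supplements". Acid-reducing drugs follow in the same sentence; opioids are not named. Section 7.2 uses the acid-reducing drugs in its pain subgroups, but links no preoperative medication to an opioid endpoint.

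**The concern.** A patient who takes an opioid at home and has it prescribed again on discharge would be scored as an event in either arm, if the endpoint is any discharge opioid. The study infusion ends at extubation and is unlikely to change whether such a prescription is renewed. Each of these patients adds an event to both arms alike and pulls the two proportions together. A real opioid-sparing effect would look smaller than it is among the patients in whom it could occur.

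The two in-hospital endpoints (intraoperative use and postoperative consumption) may also be affected. If preoperative users consume different amounts, which the protocol does not say, the unadjusted comparison carries extra between-patient variation. Because the discharge endpoint is undefined, the choice between any and new prescriptions could also be made after the data are seen.

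**Working it through.** **Figures in the plan.** Section 7.1 sizes the trial for pain only: 45 per group, and 45/(1 − 0.10) = 50 after dropout. It gives no rate, effect or power for discharge prescription and no share of home opioid users, so there is no figure to reproduce for this endpoint.

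**Inputs.** From the documents: 50 per arm (7.1), 1:1 allocation (5.3), two-sided 0.05 (7.2). Assumed: a share f of each arm is on a home opioid that is always re-prescribed and never increased; among the others, the discharge rates are p_C (control) and p_M (magnesium).

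**Formulas.**
- Any prescription: the rates are f + (1−f)p_C and f + (1−f)p_M. The difference is (1−f)(p_C − p_M), and the relative risk moves toward 1.
- New or increased prescription, home users scored no: the rates are (1−f)p_C and (1−f)p_M. The difference is again (1−f)(p_C − p_M), but the relative risk is p_M/p_C, as in non-users.
- Patients with no preoperative opioid use only: the rates are p_C and p_M, with 50(1−f) per arm. Both measures are restored.

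**Worked case, p_C = 50%, p_M = 20%, f = 10%.**
- Any: 0.10 + 0.90 × 0.50 = 0.55 and 0.10 + 0.90 × 0.20 = 0.28; difference 0.27; relative risk 0.28/0.55 = 0.51.
- New or increased: 0.45 and 0.18; difference 0.27; relative risk 0.40.
- No home opioid: 0.50 and 0.20 with 45 per arm; difference 0.30; relative risk 0.40.

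**Power at 50% vs 20%**, by exact binomial enumeration of the uncorrected chi-square test:

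| f | Difference, any or new (points) | Relative risk, any | Power, any | Power, new or increased |
|---|---|---|---|---|
| 0 | 30 | 0.40 | 0.895 | 0.895 |
| 5% | 28.5 | 0.46 | 0.849 | 0.870 |
| 10% | 27 | 0.51 | 0.802 | 0.842 |
| 20% | 24 | 0.60 | 0.699 | 0.779 |

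**Sensitivity to the assumed rates**, f = 10%, same method:

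| Rates in non-users | Power, any (50 per arm) | Power, new or increased (50 per arm) | Power, no home opioid (45 per arm) |
|---|---|---|---|
| 50% vs 20% | 80% | 84% | 87% |
| 80% vs 50% | 84% | 80% | 87% |
| 30% vs 10% | 53% | 68% | 69% |

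At high rates the redefinition loses power against the any-prescription endpoint; at lower rates it gains. The analysis without home users has more power than the any-prescription comparison in all three rows.

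**Second check.** Borrowing 60% vs 30% from the pain assumption, with 45 per arm and the normal approximation, power for any prescription is 82.8%, 78.2%, 73.4% and 63.4% at f = 0, 5, 10 and 20%. The direction is the same.

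**The case against.** Several points on the other side stand.

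- **No counting rule is stated.** A reader might infer that the protocol counts a continued home opioid as a postoperative one. It does not say so. The dilution follows only under the any-prescription reading, which nothing rules out.
- **Yes/no is itself an inference.** The same sentence of 7.2 assigns chi-square or Fisher's test to intraoperative usage and postoperative consumption, and continuous variables then go to the Mann–Whitney test. Yes/no is the natural reading for a prescription, but the text does not settle it.
- **Home opioids may already be captured.** The list in 5.6 is introduced as examples, so opioids could fall within it. That makes the remedy cheaper, but the analysis would still make no use of the data.
- **No directional bias.** A reader might infer that an imbalance in home users would pass as a drug effect. With 50 per arm and an assumed 10% home use, the arms differ by at least four such users in about 24% of trials. But allocation is randomized and the error rate of the unadjusted test already allows for this. The cost is precision.
- **Redefinition is not a full cure.** It leaves the risk difference at (1−f) of its value in non-users and can lower power.
- **Symptoms.** The background says "Pain management has largely been based on opioids, which may contribute to worsened symptoms associated with achalasia". A reader might infer that preoperative users differ on symptom outcomes. The sentence is about pain management and does not mention home users, and 6.2.1 collects the symptom questionnaire before surgery.

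Enrolling all comers and comparing them as randomized is a legitimate choice. None of these points supplies the missing definition or an analysis that accounts for home use.

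**Conclusion.** The point holds as a gap in definition and analysis of secondary endpoints. Opioid users are eligible, and the discharge endpoint makes no reference to home use. Read as any prescription (yes/no), it loses a fraction f of the risk difference for every f above 0. Under the assumed 50% vs 20% and 50 per arm, that is 1.5 to 6 points and about 5 to 20 points of power for f between 5% and 20%. The true size cannot be found from the documents. It depends on unstated home use and discharge rates, and on the assumption that every home opioid is re-prescribed.

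The documents do not support a claim of bias toward either arm or of any effect on the primary endpoint or its sample size. It is an inexpensive improvement that is worth making.

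**What to change.** 1. **5.6:** name opioids (drug and daily dose) among the preoperative medications, recorded before surgery.
2. **7.2:** prespecify, beside the all-randomized comparison, an analysis of the three opioid endpoints in patients with no preoperative opioid use, or one adjusted for preoperative use. The restriction uses a baseline variable, so the comparison remains randomized, and it restores both the risk difference and the relative risk for those patients.
3. **3.3, carried into 7.2:** define the discharge endpoint as a new or increased opioid prescription relative to recorded home use, scored yes/no. The reason is that it measures what treatment can change and keeps the relative risk undiluted. Do not justify it as restoring the risk difference or as always raising power.

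The cost is one item on a medication history already being taken, some wording, slightly fewer patients in the restricted analysis, and a home-versus-discharge dose comparison for the home users. Eligibility, treatment, visits and sample size do not change.

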6.2 Day of surgery

- 6.2.1 In the preoperative holding area, all enrolled patients will have preoperative plasma calcium and magnesium levels drawn and complete the esophageal symptoms questionnaire (ESQ), a validated survey to assess symptoms of dysphagia, globus, and reflux.

6.2.2 The patient will proceed to the OR for anesthetic care.

- 6.2.2.1 Patients will undergo rapid sequence induction of general anesthesia. In the control group, the anesthesia team will use ketamine, propofol, succinylcholine, and esmolol and/or opioids at their discretion. In the treatment arm, the anesthesia team will use ketamine and propofol using lean body weight (LBW) dosing, and succinylcholine at total body weight (TBW) dosing. After endotracheal tube placement and confirmation, sevoflurane in air and oxygen will be used for maintenance of general anesthesia. The anesthesiologist will ensure adequate neuromuscular relaxation throughout the case.

- 6.2.2.2 In the treatment arm, the anesthesia team will prepare a magnesium sulfate infusion within a 20 ml syringe. Patients will receive a magnesium sulfate bolus of 50 mg/kg lean body weight over 15 minutes, followed by a magnesium sulfate infusion at 25 mg/kg/hr when the endoscopist begins mucosal incision. In addition, the patients will receive dexamethasone 0.1-0.2 mg/kg at the start of case, and ondansetron 4 mg at the end of case. The magnesium infusion will be discontinued at extubation. After surgery, patients will be admitted to the postanesthesia care unit. For mild pain reported as a numeric score ranging from 1 to 3, acetaminophen 1000 mg IV will be offered. For pain greater than a score of 3, opioids (fentanyl and hydromorphone) will be available. For nausea and vomiting, prochlorperazine and haloperidol will be provided. Calcium gluconate and a code cart with emergency drugs and airway equipment will be made available in case of symptoms concerning for magnesium toxicity.

- 6.2.2.3 In the control arm, the anesthesia team will prepare a normal saline infusion within a 20 ml syringe. Patients will receive a normal saline bolus of 50 mg/kg lean body weight over 15 minutes, followed by a normal saline infusion at 25 mg/kg/hr when the endoscopist begins mucosal incision. Opioids (fentanyl and hydromorphone) will be administered for analgesia at the discretion of the anesthesia team. In addition, patients

CONFIDENTIAL

This document is confidential and the property of Stanford University School of Medicine.

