will receive dexamethasone and ondansetron in the aforementioned doses. After surgery, patients will be admitted to the postanesthesia care unit, where opioids (fentanyl and hydromorphone) and antiemetics (anesthesia team's discretion) will be available for further pain and nausea management.

6.3 All study participants will repeat the ESQ in the PACU when the nursing team deems the patient's recovery appropriate enough to participate.

6.4 Postoperative Day 1

6.4.1 The ESQ and serum calcium/magnesium levels will be reobtained in the morning of POD1.

7 Statistical Plan

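### As written, the 24-hour pain objective has no specified valid measure: it rests on a questionnaire described as covering dysphagia, globus and reflux, and no pain rating is scheduled on postoperative day 1.

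*Combined protocol and SAP*

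**What the plan says.** Section 2 (secondary objectives) and section 3.3 use the same formulation: the trial will assess magnesium for "decreasing postoperative pain as measured by the esophageal symptoms questionnaire score at 24 hours". No other 24-hour pain measure is named in either place.

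Section 6.2.1 introduces the ESQ as "a validated survey to assess symptoms of dysphagia, globus, and reflux". Section 6.3 adds that "All study participants will repeat the ESQ in the PACU", and section 6.4.1 that "The ESQ and serum calcium/magnesium levels will be reobtained in the morning of POD1". Section 6.4 contains nothing else.

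Section 7.2 lists the presence of spasm-related pain at 24 hours as a secondary outcome, to be tested by chi-square or Fisher's exact test. It then states: "Comparisons of postoperative pain between the two groups at time 0 h and time 24 h will be analyzed", by the Mann-Whitney U test. It also plans a post hoc analysis relating postoperative magnesium levels to whether spasm-related pain is present at 24 hours. The synopsis lists 24-hour pain and ESQ results as two distinct secondary outcomes.

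**The concern.** The endpoint is pain, but the instrument assigned to it is described by the protocol as measuring other symptoms. The statistical section then assumes pain data at 24 hours that the procedures do not tell anyone to collect.

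The risk is misinterpretation. If the team follows sections 3.3 and 6.4.1 literally, a similar ESQ score in the two arms would be reported as no effect of magnesium on 24-hour pain. A lower score driven by dysphagia, globus or reflux would be reported as pain relief. Neither conclusion follows from such a score. If the team instead follows section 7.2, it must find a 24-hour pain variable after the fact, choosing its source, time window and cut-off once data exist.

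**Working it through.** The plan gives no effect size or power for the 24-hour outcome, so there is no figure to reproduce. The sample size in section 7.1 does not bear on this point: section 7.2 places the primary outcome at 0 h. The check is a comparison of sections.

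1. **Construct.** Sections 2 and 3.3: postoperative pain at 24 hours.
2. **Instrument.** Same sections: the ESQ score, meaning the score itself and not a named item or subscale.
3. **Content of the instrument.** Section 6.2.1 names three symptoms, and pain is not one of them. The ESQ validation paper in the reference list carries the same three in its title. The attachments list a sample ESQ, but its items are not in the text available.
4. **Data scheduled on day 1.** Section 6.4.1: ESQ, serum calcium, serum magnesium.
5. **Pain scores elsewhere.** Section 3.2 speaks of "esophageal spasm-associated pain as measured by subjective pain scores and the esophageal symptoms questionnaire score". This is the primary endpoint, and it comes with no scale, time point or collection step. The only numeric score in the procedures is in 6.2.2.2: "For mild pain reported as a numeric score ranging from 1 to 3, acetaminophen 1000 mg IV will be offered". That score guides analgesia in the recovery unit rather than serving as a study assessment. It appears in the treatment-arm paragraph only; the control-arm text in 6.2.2.3 gives no score.
6. **Data the analysis needs.** Section 7.2 needs a binary variable (spasm-related pain present or absent at 24 hours) and an ordered variable (pain at 24 hours, for the rank test).
7. **Link between 4 and 6.** None is given. No section states a 24-hour pain scale, a cut-off for counting pain as present, a rule for attributing it to esophageal spasm, or a way to derive pain from the ESQ.
8. **Timing.** Section 6.4.1 asks for the assessment in the morning, whereas 3.3 and 7.2 speak of 24 hours. The morning is not tied to the end of surgery, so the actual interval will vary and no window is set.

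Extent: one of the four secondary objectives in section 2; three analyses in section 7.2 (binary outcome, rank test, post hoc magnesium-level analysis); and both arms, 50 + 50 = 100 planned participants.

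**The case against.** The strongest reply is that the documents, read together, point to a separate 24-hour pain score that was intended and simply not carried through. The synopsis lists 24-hour pain apart from ESQ results, section 7.2 analyses it, and pain scores are named for the primary endpoint. Section 6 is not an exhaustive data list either: it schedules no recording of postoperative opioid consumption or discharge prescriptions, yet both are endpoints. Section 9.2 counts hospital records among source documents. This stands to a point. It shows that the source is unspecified rather than that no pain data will exist. It does not remove the conflict, because sections 2 and 3.3 name the ESQ and no section names chart scores. Routine chart scores also need not identify esophageal spasm pain.

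A second reply is that the ESQ may contain a pain item. That cannot be excluded. But the endpoint is the ESQ score, and no section isolates such an item.

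A third is that sections 1.2 and 1.4 link esophageal pain with regurgitation and reflux, so an ESQ difference is not irrelevant to the hypothesis. That is fair, and a reason to keep the ESQ as an endpoint. It does not make it a pain scale.

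A reader might go further and infer that the ESQ is invalid here because every patient has a myotomy and a tracheal tube between the preoperative and later questionnaires, and section 1.1 describes the procedure as a "safe and effective surgery for achalasia and other esophageal motility disorders". The documents do not support that. Both arms share the surgery and the intubation, so randomization balances their effects in the between-arm comparison. They may add noise, but no figure shows how much. Section 7.2 does not specify a change-from-baseline ESQ analysis.

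**Conclusion.** The concern holds in this form: as the plan is written, the 24-hour pain objective has no specified valid measure, and the 24-hour pain analyses have no stated data source. A reader might infer that the objective cannot be answered at all. That is too strong, since the ESQ items are not reproduced and ward pain scores may exist. Neither, however, is planned for use.

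The conclusion rests on two things: the protocol's own description of the ESQ, and section 6.4.1 being the only description of day 1 assessments. It would change if the sponsor could show that the ESQ has a pain item intended as the 24-hour endpoint, or that a defined chart score was always meant.

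The matter is separate from how the 0 h primary outcome is defined: settling that would still leave day 1 without a pain rating. It deserves correction because a specific esophageal pain rating not asked on day 1 cannot be reliably recovered later.

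**What to change.** - **Section 6.4.1:** add one 0-10 numeric rating of retrosternal/esophageal pain, in both arms, asked just before the ESQ and within a stated time window after surgery.
- **Synopsis and sections 2, 3.3 and 7.2:** define the 24-hour pain endpoint on that rating. Use the raw score for the Mann-Whitney test. For the yes/no outcome, prespecify the cut-off at which spasm-related pain counts as present; the rating alone does not define it.
- **ESQ:** keep the score as a separate secondary endpoint for esophageal symptoms, and make no pain claim from it.
- **Preoperative rating:** optional, since no analysis in section 7.2 uses baseline pain.

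The cost is a protocol amendment and one extra CRF item at a contact that already takes place. No additional visit or participants are needed.
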